## **4.2. Participating Sites**

Patients will be exposed to the intervention or usual care at two participating ED's in Carolinas HealthCare System. The following Carolinas Healthcare System ED sites will be participating in this project.

- Carolinas HealthCare System Pineville
- Carolinas HealthCare System Union

## **4.3. Inclusion\Exclusion Criteria**

### **4.3.1. Inclusion Criteria**

Eligible patients must meet each of the following criteria:

- Present to an ED at participating sites
- Completed a telepsychiatric consult as captured in the electronic medical record
- Telepsychiatric consult completed Monday through Friday during the Navigator's potential hours of operation
- $\geq 18$  years of age at time of ED admission

### **4.3.2. Exclusion Criteria**

No exclusion criteria.

## **4.4. Evaluable Population**

Patients included in the evaluable population for this project, will have their data inform the final outcomes assessment. All patients who meet the inclusion criteria and have a completed telepsychiatric consult will be assessed. Evaluation will be by intent to treat. All patients in the both arms will be assessed for the primary outcome. Patients admitted directly from the ED or have neurocognitive disabilities from the intervention arm will not receive services from the BH-VPN. Patients in either arm have the following potential disposition: (admission to the hospital for medical reasons, admission to a behavioral health facility by voluntary or involuntary commitment, discharge from the ED, or death).

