### **4. SUBJECT AND SITE SELECTION**

#### **4.1. Accrual**

As part of current care, patients are identified by an ED physician in the ED as needing psychiatric evaluation, and a referral is made to the telepsychiatric provider for a virtual consult. Patients are eligible to be included in analysis for the project if they meet the inclusion/exclusion criteria and the telepsychiatric consultation occurs during potential BH – VPN hours. We will accrue patient data for evaluation during a period starting in June 2017. Based on data from 2016, we estimate 500 patients will complete a telepsychiatric consult in a 6-month period during potential BH-VPN hours of operation. Patients will not be accrued on days where the navigators could not potentially be available, such as nights, weekends, and holidays.

Once a patient is in the intervention arm, the patient remains in the intervention arm until 45 days, or if there is a failure to contact (4 phone calls in 12 days), if the patient becomes enrolled with a case management program, declines services, or if the patient dies. After 45 days, a patient is eligible to be re-enrolled in either arm of the study.

A patient remains in the control arm for 45 days unless the patient returns to the ED on a day where patients are being randomized to the intervention arm.

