## **5.2. Randomization and Allocation**

Randomization for the purposes of this project, will be based on days the Navigators are available to treat patients who've completed their telepsychiatric consult per the BH-VPN or usual care. Patients may be in the ED for multiple days. Their enrollment status depends on the day and time of their initial telepsychiatric consultation. Navigation will only be available for those patients whose consult occurs during intervention day/times. As part of the research design and rollout of this project, randomization will occur at the day level with the days being identified as intervention or usual care days for the duration of the study. We expect an average of 3.7 patients seen daily for both hospitals combined. Patients will accrue in both arms of the study Monday through Friday during the hours of operation. Patients will not be accrued on days where the navigators are not available such as weekends, nights, and holidays.

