## 6.2. Statistical analysis

All analyses will follow intention to treat such that patients will be analyzed based on the allocated intervention on the day of their ED visit (BH-VPN or treatment as usual). We will compare the two groups on age, sex, suicide ideation, and neurocognitive disorders to assess for balance, which is inferred with randomization.

The primary outcome, inpatient admission  $\leq 5$  days, will be compared between the two groups of patients using a chi-square test. We will explore differences by site by conducting stratified analysis by hospital. We will attempt to adjust for the correlation among patients seen on the same day using a generalized linear mixed model with a log link and random effect for day, nested within hospital. If convergence problems arise due to small sample sizes, we will collapse by week rather than day. We will also control for hospital as a fixed effect in the model. Results for group comparisons will be presented with odds ratios and 95% confidence intervals.

Secondary outcomes are 45-day post discharge utilization (yes/no), 90-day post discharge utilization (yes/no), QCC defined 30-day readmission (yes/no), and patient centric 30-day readmission (yes/no). Each of the secondary outcomes are dichotomous and will be compared using the same approach as the primary outcome. All tests will be two sided and the data will be analyzed using SAS Enterprise Guide version 6.1. For all outcomes, we assume if there are no visits in the CHS electronic medical record that the value for having a visit is null; therefore, there will be no missing data for the primary or secondary outcome measures.

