### 9.1. Protocol and Pathway Training

Background, protocol and process steps will be presented to psychiatrists and nurse practitioners who will be providing virtual psychiatric consultations. The role of virtual patient navigator and randomization scheme will be presented so expectations are clear that this is not available every day/time or weekends. This will be presented at the Department of Psychiatry meeting, which includes Emergency and Telepsychiatry Departments. Attendees may also include providers, who at some point may see patients who have been through this pathway, but will not be directly involved in providing evaluations. Education will be provided to the emergency department staff involved in this project, so that they are aware of the process and the role of the virtual patient navigator.

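### Patients enter the analysed population through a referral and a completed consult that follow the day's allocation, so randomising days does not guarantee balance in the group compared.

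*Combined protocol and SAP*

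**What the plan says.** Section 5.2 allocates whole days: "randomization will occur at the day level with the days being identified as intervention or usual care days for the duration of the study". Within a day, Section 4.1 describes how a patient reaches the trial: "patients are identified by an ED physician in the ED as needing psychiatric evaluation, and a referral is made to the telepsychiatric provider". Section 4.3.1 makes the outcome of that referral an eligibility condition: "Completed a telepsychiatric consult as captured in the electronic medical record". Section 4.4 analyses the patients so defined: "All patients who meet the inclusion criteria and have a completed telepsychiatric consult will be assessed".

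No masking of ED physicians and no concealment of the day list is described. Under Section 9.1 the randomization scheme is presented to the psychiatrists and nurse practitioners who give the consults. For the EDs it says: "Education will be provided to the emergency department staff involved in this project, so that they are aware of the process".

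The safeguards are the intention-to-treat statements in 4.4 and 6.2 and a comparison in 6.2 of age, sex, "suicide ideation, and neurocognitive disorders to assess for balance, which is inferred with randomization". The planned model adds hospital and a random day effect. No referral rate by arm and no denominator fixed before referral is planned.

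The assignment rule is also worded in two ways. Section 5.2 says "Their enrollment status depends on the day and time of their initial telepsychiatric consultation", while Section 6.2 says "patients will be analyzed based on the allocated intervention on the day of their ED visit". As patients may stay in the ED for several days, these can point to different days and must be reconciled.

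**The concern.** When clusters are randomised and patients are identified afterwards by staff who may know the allocation, the two groups can differ before treatment starts. Here the cluster is a day and the identifying step is the referral and completed consult.

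The protocol's own rationale suggests why referral might differ. Section 2 reports that providers often admit because outpatient resources are scarce and nobody is available to arrange follow-up. On intervention days the consult is the route to a navigator who can do that. A physician who knows the navigator is available could refer some patients, likely to go home, who would not otherwise have had a consult. Those patients would lower the navigator-day conversion rate with no admission avoided.

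Intention to treat guards against exclusions after entry, not against differential entry. The balance check covers four variables among patients already selected, so it can miss a shift in severity. A change in disposition after the consult is a different matter: that is part of the intended effect, not bias. The point concerns only who is referred and whose consult is completed.

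**Working it through.** **1. The plan's own figure.** Inputs from Section 6.1: 50% against 35%, 85% power, alpha 0.05 (two-sided per 6.2). The usual two-proportion formula gives 194 per arm. With the continuity correction it gives 207 per arm, or 414 in total, as stated. Then 414 × 1.1 = 455.4, rounded up to 456, or 228 per arm. The sample size is not in question.

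**2. How many patients could be referred with the arm visible.** Suppose staff learn the arm only from the first patient who reveals it that day, with Poisson arrivals and a mean of m revealing patients per ED per day. Among patients of that type, the share arriving after the first is 1 − (1 − e^−m)/m. The same value is the share of all patients arriving after that first one.
- If every consulted patient reveals the arm, m = 2 (Section 6.1): 1 − (1 − e^−2)/2 = 57%.
- Navigators approach only patients with discharge recommended and no neurocognitive disability (5.3). If about half are approached (an assumption in line with the 50% admission rate), m = 1: 1 − (1 − e^−1) = 37%.
- With 3.7/2 = 1.85 patients per ED (5.2) and half approached, m = 0.925: 35%.

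**3. Size of a mix shift.** Let x be the extra navigator-day referrals as a fraction of the usual number, and q their conversion rate. The documents give neither. With no navigation effect the navigator-day rate is (0.50 + x·q)/(1 + x). Rejection probabilities use the normal approximation for two proportions with an effective 228/1.1 = 207.3 per arm.

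| x | Reading | q | Navigator-day rate | Spurious reduction | Rejection |
|---|---|---|---|---|---|
| 7.4% | 20% rise within the 37% (0.20 × 0.37) | 10% | 47.2% | 2.8 points | 9% |
| 7.4% | same | 30% | 48.6% | 1.4 points | 6% |
| 20% | 20% rise over all patients | 10% | 43.3% | 6.7 points | 27% |
| 20% | same | 20% | 45.0% | 5.0 points | 17% |
| 20% | same | 30% | 46.7% | 3.3 points | 10% |

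Example: (0.50 + 0.2 × 0.1)/1.2 = 0.433. The pooled rate is 0.467, the null SE 0.0490 and the alternative SE 0.0489, so (0.0667 − 1.96 × 0.0490)/0.0489 = −0.60 and the probability is 27%. Setting x = 0 returns 5%.

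The x = 20% rows need the arm to be known throughout the day, or a rise of 0.20/0.37 = 54% within the visible share.

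**4. Direction.** If the extra patients convert above 50%, the sign reverses. With x = 20% and q = 70% the rate is (0.50 + 0.14)/1.2 = 53.3%, which would hide 3.3 points of benefit.

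**5. What a count of consults could detect.** Expected consults per arm are 60 days × 3.7 = 222. On a Poisson log rate ratio with SE √(1/222 + 1/(222(1 + x))), power is 18%, 52% and 84% for a 10%, 20% and 30% excess. Day-to-day overdispersion would lower these.

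**The case against.** Four arguments on the other side deserve an answer.

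**Knowledge of the arm is not stated.** A reader might infer from Section 9.1 that ED physicians know the day's arm when they refer. The text does not say so. The scheme is presented to the clinicians who receive referrals, while ED staff are taught the process and the navigator's role. Referral is existing care for patients judged to be in crisis, and nothing shows that its threshold will move. This stands, and it limits the point to what could happen.

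**The exposure is easily overstated.** Dividing 2.7 by the 3.7 daily patients suggests that 73% are referred after the arm is known. That pools two hospitals, although an approach at one ED does not reveal the arm at the other, and it treats every first patient as revealing the arm. The per-ED figure is roughly 35% to 57%, and overlapping stays would lower it. This stands.

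**There may be few unreferred patients.** Section 2 gives 14,293 Metro behavioral-health ED visits in 2016 and 21 Metro EDs. Two average sites would see 14,293/21 × 2 × 0.5 = 681 in six months, about 486 on weekdays. The plan expects 500 consults in operating hours alone, so the two sites cannot be average on these figures and the check settles nothing. The size of the pool remains unknown and could cap x.

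**A wider denominator is a weak test.** Suppose behavioral-health visits number two to three times the consults and the other visits convert at 10% (both assumptions). A true 15-point effect becomes 30.0% against 22.5%, or 23.3% against 18.3%: 7.5 or 5.0 points. Power is then 69% or 58% at a design effect of 1.1, and 62% or 46% if it grows with cluster size to 1.3 or 1.5. This stands. A benefit missing from that analysis would not show that navigation failed, so it must not override the primary result.

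**Conclusion.** The point holds as a gap in protection against bias, and should be addressed. Entry to the analysed population depends on clinical steps taken after allocation in an open design, and nothing planned would show whether those steps differed by arm. Balance in that subset cannot be inferred from randomising days.

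The illustrative size is a spurious reduction of about 1.4 to 6.7 points against a 15-point target, with rejection of about 6% to 27% instead of 5%. It rests on assumed values: 7% to 20% extra referrals converting at 10% to 30%, no true effect, a 50% base rate, 228 per arm and a design effect of 1.1. The upper end needs the arm to be known more widely than the first-approach mechanism implies, or a large change in referral.

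A reader might go further and conclude that the trial is biased in favour of navigation. The documents do not support that: they give no evidence that referral will differ, and the shift could run either way.

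**What to change.** Keep the consulted population as primary. In Section 6.2, end the balance sentence at neurocognitive disorders, dropping the clause that infers balance, and pre-specify two additions, cross-referenced from 4.4:

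1. Completed consults per day, and the proportion of behavioral-health ED visits referred, by arm, with 95% confidence intervals that allow for day-to-day variation.
2. A supportive repeat of the primary comparison in all adult behavioral-health ED visits at the two sites arriving on randomised weekdays during operating hours, consulted or not. Identify the visits from a field recorded before referral, if one is available (the documents name none). Set the arm by day of arrival and use the same day-level model.

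State in advance that if referral volume differs by arm, or the two analyses disagree, the primary result may partly reflect case mix and will be interpreted with caution. Reconcile the assignment wording in 5.2 and 6.2 at the same time.

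The cost is plan wording and one further query of existing records. Section 2 shows the system already counts behavioral-health visits, and Section 6 already has a monthly volume summary. No extra patients, visits or staff are needed. The drawbacks are a diluted effect in the wider denominator, some misclassification where arrival and consult fall on different days, and a consult count that will often miss a moderate excess.

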## **5. OVERALL DESIGN**

### **5.1. Outcome Variables**

#### **5.1.1. Primary Outcome Variable**

The primary outcome variable is ED to inpatient or observation conversion. This is a patient that presents to either of the two CHS ED sites and then within 5 days of their ED discharge are admitted for any reason to a CHS facility as an inpatient or observation patient. In the electronic medical record, 2 hospital encounters are shown, the ED encounter and the inpatient\observation hospital encounter. Based on data from 2016 at CHS, most patients discharged from the ED who convert to an admission do so within 2 days of their ED discharge. Five days were chosen to maximize the conversions attributed to the ED encounter.

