#### **5.1.2. Secondary Outcome Variable(s)**

Secondary outcome variables of the evaluation include:

Examining the BH-VPN's effect on additional patient outcomes as compared to usual care, such as

- a. CHS QCC defined 30-day readmission rate. This is a readmission rate among patients with an inpatient readmission to the same CHS facility as the index encounter. This measure applies to patients that have a hospital admission subsequent the ED encounter.
- b. The patient-centric defined 30-day readmission rate. This is a readmission rate among patients with an inpatient or observation readmission to any CHS facility. This measure applies to patients that have a hospital admission subsequent the ED encounter.
- c. 45-day post ED discharge utilization. Utilization is defined as an inpatient, observation, or ED encounter at a CHS facility.
- d. 90-day post ED discharge utilization. Utilization is defined as an inpatient, observation, or ED encounter at a CHS facility.

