## 6.1. Sample size analysis and statistical analysis

We are conducting the study for about 6 months leading to approximately 6 months\*4 weeks\*5 days=120 days with 60 days allocated to intervention and 60 allocated to treatment as usual. This study is designed to detect a 15% absolute reduction in the inpatient admission within 5 days of index ED presentation with the usual care group assumed to have a 50% inpatient admission rate (internal report). We will have 85% power to detect this reduction with a total sample size of 414 ( $\alpha=0.05$ ) using a Chi-square test for independence. We will not need to adjust for attrition as the primary outcome of inpatient admission <5 days is obtainable from electronic health records for all individuals. To account for the possible correlation among patients seen in the ED on the same day, we have inflated the sample size by 10% assuming the average number of patients per ED per day is 2 and the intra-class correlation coefficient=0.1 (Design effect=1+(2-1)ICC). Therefore, our target sample size is N=456.

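### The primary endpoint conflicts between sections: 5.1.1 counts inpatient or observation admission from ED discharge, while 6.1 and 6.2 use inpatient admission only, timed from ED presentation or from no stated point

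*Combined protocol and SAP*

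**What the plan says.** Section 5.1.1 is the only place that defines the primary outcome in full. A patient is an event if they "within 5 days of their ED discharge are admitted for any reason to a CHS facility as an inpatient or observation patient". It adds that, in 2016 data, "most patients discharged from the ED who convert to an admission do so within 2 days of their ED discharge", and that five days was chosen to capture as many conversions as possible.

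Section 6.1 describes a different event: "This study is designed to detect a 15% absolute reduction in the inpatient admission within 5 days of index ED presentation". The control rate is introduced "with the usual care group assumed to have a 50% inpatient admission rate (internal report"). Later in the same paragraph it says "the primary outcome of inpatient admission <5 days is obtainable from electronic health records for all individuals", with a strict inequality and no starting point.

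Section 6.2 opens its analysis text with "The primary outcome, inpatient admission", followed by a limit of at most 5 days. It mentions neither observation stays nor a starting point.

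The Protocol Summary (objectives and statistical analysis rows), 1.1 and 1.2 refer only to inpatient conversion, with no window.

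Elsewhere the protocol separates the two kinds of stay. In 5.1.2 the QCC measure is defined thus: "This is a readmission rate among patients with an inpatient readmission to the same CHS facility as the index encounter". The patient-centric measure is defined thus: "This is a readmission rate among patients with an inpatient or observation readmission to any CHS facility". Section 5.2 notes that an ED stay can last several days.

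**The concern.** These texts state two different rules for the one primary comparison. A programmer working from 6.2 would code an observation-only patient as a non-event; one working from 5.1.1 would code the same patient as an event. The data come from electronic records and may be extracted after participation ends (section 6), so both versions can be computed, and nothing fixed in advance says which is primary.

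The planning rate has the same problem. If 5.1.1 governs, the documents do not show that 50% is the control rate for that event, so the stated power is not yet tied to the endpoint to be tested.

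**Working it through.** **1. The definitions side by side**

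| Place | Event | Time origin | Limit |
|---|---|---|---|
| 5.1.1 | inpatient or observation | ED discharge | within 5 days |
| 6.1, design sentence | inpatient | ED presentation | within 5 days |
| 6.1, attrition sentence | inpatient | none | <5 days |
| 6.2 | inpatient | none | ≤5 days |
| Summary, 1.1, 1.2 | inpatient conversion | none | none |

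Two constructed patients show that the rules differ.
- An observation stay one day after ED discharge counts under 5.1.1 and not under 6.1 or 6.2.
- An inpatient admission 4 days after discharge from a 2-day ED stay counts under 5.1.1 but falls on day 2 + 4 = 6 from presentation, outside the 6.1 window.

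Presentation precedes discharge, so moving from the 5.1.1 origin to the 6.1 origin can only remove events.

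**2. Reproducing the plan's sample size**

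Inputs: p1 = 0.50, difference d = 0.15 (so p2 = 0.35), power 85% and α = 0.05, from 6.1; two-sided testing, from 6.2; equal arms (60 and 60 days), from 6.1. The mean rate is p̄ = 0.425.

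n = [1.960·√(2p̄(1−p̄)) + 1.036·√(p1(1−p1) + p2(1−p2))]² / d²
= [1.960·√0.48875 + 1.036·√0.4775]² / 0.0225 = 193.5 per arm.

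With continuity correction: n′ = (n/4)·[1 + √(1 + 4/(n·d))]² = 206.6, so 207 per arm and 414 in total. The design effect is 1 + (2 − 1)·0.1 = 1.1, and 414 × 1.1 = 455.4, so 456. Both stated figures reproduce. Without the correction the total before inflation would be 388, so the plan evidently used it.

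**3. Power if the rates belong to a different event**

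With n′ = 207 effective patients per arm, n* = (n′ − 1/d)²/n′ and
power = Φ{[d·√n* − 1.960·√(2p̄(1−p̄))] / √(p1(1−p1) + p2(1−p2))}.
The uncorrected version puts 207 in place of n*. The documents give no observation share, so every row after the first is an assumption.

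| Scenario | Rates | Corrected | Uncorrected |
|---|---|---|---|
| As planned | 50% v 35% | 85% | 87% |
| Observation adds 5 points to both arms | 55% v 40% | 84% | 87% |
| Observation adds 10 points to both arms | 60% v 45% | 84% | 87% |
| Observation adds 15 points to both arms | 65% v 50% | 85% | 87% |
| Difference 13.5 points | 50% v 36.5% | 76% | 79% |
| Difference 12 points | 50% v 38% | 66% | 69% |
| Lower control rate, same 30% relative reduction | 40% v 28% | 70% | 73% |

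The 13.5- and 12-point rows would arise if 10% or 20% of the planned 15-point fall turned into observation stays (15 × 0.9 and 15 × 0.8). The last row would arise if the 50% already included observation stays, the inpatient-only rate were 40%, and the effect were relative (15/50 = 30%; 40% × 0.7 = 28%).

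**4. Size of the time-origin difference**

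At 228 per arm, expected events are 228 × 0.50 + 228 × 0.35 = 114 + 79.8 = 193.8. If 1%, 2% or 5% of these fall inside the 5.1.1 window but outside the 6.1 window, equally in both arms (assumption), about 1.9, 3.9 or 9.7 patients change status. That is 0.4% to 2.1% of 456. Corrected power is then 84%, 84% or 82%.

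**The case against.** The best defence is that 5.1.1 governs. It is the section on the primary outcome variable, the only one that gives event, window and facility together, and the only one that explains the choice of five days. On that view 6.1 and 6.2 merely refer to the outcome in shorthand. This is a reasonable reading, but no text states it, and 5.1.2 shows that the authors distinguish inpatient from observation when they mean to. Every other statement of the primary outcome says inpatient, as does the only planning rate, so the opposite reading can also be defended.

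A second defence is that little changes in practice. For the time origin and the stray strict inequality this largely stands: 5.1.1 reports that most conversions come within 2 days of ED discharge, and the assumed range moves at most about 10 patients. For the event type it cannot be judged, because the observation share is not given.

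A reader might infer that the sample size is wrong. The documents do not support that: the arithmetic reproduces, and power barely moves if the 15-point difference carries over. A reader might also infer that power can fall only if prevented inpatient stays become observation stays. That is too narrow, as the 40% versus 28% case shows, and no passage suggests such a shift in any case.

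**Conclusion.** The conflict is literal and concerns the single primary test, so the plan is wrong as written and must be reconciled before analysis. The case rests on two incompatible event definitions, not on a demonstrated loss of power. The time origin and the inequality sign are wording corrections.

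The 85% power is documented for inpatient admission only. It holds at about 84–85% for the 5.1.1 event if the absolute difference stays at 15 points and observation adds 5 to 15 points equally to both arms. It would be about 66–76% under the smaller differences above (69–79% without continuity correction). All of those rates are assumptions; which one applies depends on what the internal report measured.

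**What to change.** Use one definition of event type, time origin and boundary throughout. Section 5.1.1 is the natural choice because it is the only complete one. Carry it into 6.1, 6.2, both Summary rows (objectives and statistical analysis), 1.1 and 1.2, and replace the strict inequality in 6.1. If the sponsor intends inpatient admission only, amend 5.1.1 instead, before analysis.

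State explicitly whether a direct admission from the ED counts. Section 4.4 suggests that it does, since it mentions such patients and assesses everyone for the primary outcome, but 5.1.1 does not say so.

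Report the other event type as a sensitivity analysis. Check which event and window the internal 50% rate reflects, and restate the power if they differ from the chosen definition.

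The cost is wording in those sections and one look at the internal report. No new data are needed, because inpatient, observation and ED encounters at CHS facilities are already required for the utilization outcomes in 5.1.2.
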